3.3.1.2 Exclusion Criteria

A participant is not eligible if any of the following exclusion criteria are present.

1. Participant is in another investigational study and actively receiving study therapy.
2. Participant is unable to comply with study procedures or follow-up visits.
3. Participant is already taking vitamin A palmitate supplements $\geq 8,000$ IU.
4. Participant has a history of vitamin A deficiency.
5. Participant has a condition that, in the opinion of the investigator, would preclude participation in the study (e.g., unstable medical status including blood pressure and glycemic control).
6. Participant has a history of hepatitis or liver failure.
7. Participant has chronic gastrointestinal disease.
8. Participant will be excluded if the participant has serologic evidence of an active hepatitis infection.
9. Participant was in Cohort 1 and took his/her last dose of vitamin A palmitate less than two months prior to enrolling in Cohort 2.

3.3.2 Study Eye Eligibility Criteria

The participant must have at least one eye meeting all inclusion criteria and none of the exclusion criteria listed below.

3.3.2.1 Study Eye Inclusion Criteria

1. The eye must have a best-corrected Early Treatment Diabetic Retinopathy Study (ETDRS) visual acuity score better than or equal to 20/80 (i.e., equal to or better than 54 letters).
2. Participant must have at least one large druse.
3. Abnormal dark adaptation, which is defined as having an AdaptDx test with a RIT of 16 minutes or more at the screening visit. This is at least one standard deviation greater than the average normal RIT and includes room to account for variability in testing. If at any point during current testing or under a previous NEI protocol, a participant has exceeded the 40 minute test ceiling, they will have satisfied the inclusion criteria.

3.3.2.2 Study Eye Exclusion Criteria

1. Presence of advanced macular degeneration with central geographic atrophy or choroidal neovascularization.
2. Presence of definite reticular pseudodrusen.
3. An ocular condition is present (other than AMD) that, in the opinion of the investigator, might alter visual acuity during the course of the study (e.g., vein occlusion, uveitis or other ocular inflammatory disease, neovascular glaucoma, Irvine-Gass Syndrome, etc.).
4. Substantial cataract that, in the opinion of the investigator, is likely to be decreasing visual acuity by three lines or more (i.e., cataract would be reducing acuity to 20/40 or worse if eye was otherwise normal).
5. History of major ocular surgery (e.g. cataract extraction, scleral buckle, any intraocular surgery, etc.) within three months prior to study entry.
6. History of Yttrium-Aluminum Garnet (YAG) capsulotomy performed within two months prior to study entry.

3.3.2.3 Choice of Study Eye in Case of Bilateral Disease

If both eyes meet the study eye eligibility criteria described above, the following criteria will be used to select the study eye for the purposes of this investigation:

1. The eye with the better visual acuity will be chosen.
2. If both eyes have equal acuity, the right eye will be arbitrarily chosen as the study eye.

3.4 Outcomes

3.4.1 Primary Study Outcome

The primary outcome for the first cohort is the measurement of dark adaptation parameters (thresholds and kinetics) in the study eye by the following:

- Dark adaptation times and kinetic parameters (i.e., curve parameters) as measured by the AdaptDx comparing baseline and two months after vitamin A palmitate supplementation.
- Dark adaptation parameters (kinetic/curve parameters and pre-bleach thresholds) as measured by the Medmont comparing baseline and two months after vitamin A palmitate supplementation.

The primary outcome for the second cohort is the measurement of dark adaptation parameters (thresholds and kinetics) in the study eye by the following:

- Dark adaptation times and kinetic parameters (i.e., curve parameters) as measured by the AdaptDx comparing baseline and one month after vitamin A palmitate supplementation.
- Dark adaptation parameters (kinetic/curve parameters and pre-bleach thresholds) as measured by the Medmont comparing baseline and one month after vitamin A palmitate supplementation.

3.4.2 Secondary Study Outcomes

The secondary outcomes for both cohorts are changes in low luminance visual acuity (LLVA) and patient-reported outcomes as measured by the low luminance questionnaire (LLQ) comparing baseline to the following timepoints:

- Completion of supplementation (Month 2 in Cohort 1 and Month 1 in Cohort 2)
- One month after completing supplementation (Month 3 in Cohort 1 and Month 2 in Cohort 2).

The secondary outcomes for both cohorts also include the measurement of dark adaptation parameters (thresholds and kinetics) by the following:

- Dark adaptation times and kinetic parameters (i.e., curve parameters) as measured by the AdaptDx comparing baseline and post-treatment follow-up visit
- Dark adaptation parameters (kinetic/curve parameters and pre-bleach thresholds) as measured by the Medmont comparing baseline and post-treatment follow-up visit

Safety outcomes include the number and severity of systemic and ocular toxicities, AEs and infections, occurring throughout the study period.

4.0 DEFINITIONS

Treatment completion visit: The visit corresponding to completion of treatment, occurring at Month 2 in Cohort 1 and Month 1 in Cohort 2. The primary outcome is assessed at this visit.

Post-treatment follow-up visit: The final study visit which occurs one month after completion of treatment, corresponding to Month 3 in Cohort 1 and Month 2 in Cohort 2.

5.0 STATISTICAL CONSIDERATIONS

Since this is a proof-of-principle study, all analyses will be exploratory in nature.

5.1 Sample Size

A total of 18 participants, eight in Cohort 1 and up to ten in Cohort 2, may be enrolled in the study to obtain five participants for the primary outcome analysis for each cohort. No formal sample size calculation was conducted, since this pilot study will not attempt to definitively determine the safety or efficacy of this treatment.

5.2 Analysis Populations

The following analysis populations will be considered for this study:

Screened population: Includes all participants screened, regardless of eligibility determination / enrollment status. Participant disposition will be based on this population.

Enrolled population: Includes all participants enrolled in the study, regardless of compliance, follow-up, or treatment received. Demographic characteristics and compliance will be based on this population. Screen failures are not included in the enrolled population.

Primary analysis population: Includes all enrolled participants who receive investigational product (IP) through the treatment completion visit. The primary, secondary, and exploratory outcome analyses will be based on this population.

Safety population: Includes all enrolled participants who receive at least one dose of IP. All safety analyses will be based on this population.

5.3 Descriptive Statistics

For continuous parameters, descriptive statistics will include number of observations, mean, standard deviation, median, minimum and maximum. For categorical parameters, frequency and percentage of participants will be summarized.

5.4 Handling Duplicate Assessments

If participants completed assessments at both scheduled and supplementary visits, the assessments from the scheduled visit will be considered in the analysis and tabular summaries. However, if an assessment is completed only at supplementary visits, then the assessments from the most recent supplementary visit will be included in the analysis and tabular summaries. Results of all assessments, including those performed during supplementary visits, will be included in the listings.

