4.3 Study Design and Procedures

The study duration will be three months for the first cohort during which participants will be instructed to take vitamin A palmitate 16,000 IU daily by mouth for two months. In the second cohort, the study duration will be two months and the participants will be instructed to take vitamin A palmitate 48,000 IU daily by mouth for one month. In addition, there will be a screening visit between 60 days and one day prior to the baseline visit. For the first cohort, the primary outcome will be assessed at baseline versus Month 2 and the secondary outcomes will be assessed at baseline versus Month 2 and baseline versus Month 3. For the second cohort, the primary outcomes will be assessed at baseline versus Month 1 and the secondary outcomes will be assessed at baseline versus Month 1 and baseline versus Month 2. For both cohorts, visits will occur at baseline, and then monthly and as clinically indicated. The study will require five visits for the first cohort and four visits for the second cohort. All visits must be conducted within a window of \pm 14 days from the target day. At each visit, the participant will undergo a review of systems, such as an assessment of headache frequency and severity, as well as an assessment of safety variables. The tests scheduled at each visit may be split and completed within seven days (including the 7th day) from the visit date. A complete ophthalmologic examination will be performed at each visit to measure outcome variables. Participants will be screened with serum for hepatitis or hepatic dysfunction. However, for caution, we will monitor liver function tests. If participants in either cohort cannot tolerate the prescribed dose of vitamin A palmitate, they will be instructed to stop taking the supplement and they will be removed from the study.

If participants are on Coumadin® (Warfarin) at enrollment, they must visit their prescribing physician to check their Coumadin® status within two to four weeks after initiating IP to have their

Coumadin® regimen adjusted if necessary (as taking vitamin A and Coumadin® can increase the chances of bruising and bleeding.)

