12.1 Adverse Events (AEs)

AEs reported throughout the study period will be presented in a listing with details including date reported, description, severity, relatedness to IP, outcome and date resolved. Total number and percentage of participants with AEs will be summarized by cohort and overall and categorized by severity of the AE, ocular specification (ocular vs. systemic), outcome, and relation to IP (Table 12).

AEs will also be summarized by system organ class (SOC) and preferred term (PT) (Table 13). If sufficient data are present, summaries similar to Table 12 and Table 13 will be generated for all serious adverse events (SAEs).

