14.2 Best-Corrected Visual Acuity (BCVA)

Visual acuity is assessed at baseline and all follow-up visits in both eyes. BCVA with manifest refraction is scheduled to be performed at baseline and Month 2 and if a change in BCVA total letters read of ≥ 10 (≥ 0.20 logMAR) since previous visit is observed. Values from assessments performed with manifest refraction will be used for the analysis if available; otherwise, values from assessments performed without manifest refraction will be used.

Total letters read at each visit and change from baseline at each follow-up visit will be presented by participant for both eyes and summarized by cohort and overall as in Table 16. Participants experiencing loss of ≥ 15 letters from baseline may be withdrawn from the study at investigator's discretion. Frequency and percentage of participants presenting with a loss of ≥ 15 letters from baseline at each follow-up visit will be included in Table 16.

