14.6 Optic Nerve Papilledema, Headache, and Medication Assessment

Participants are assessed at each visit for headache and presence of optic nerve papilledema. Additionally, vitamin A palmitate consumption outside of the study is assessed at each follow-up visit. Number and percentage of participants experiencing optic nerve papilledema in each eye, headache classified by severity, and vitamin A palmitate consumption outside of the study will be summarized by cohort and overall as in Table 20; relevant information will be listed by participant.

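### SAP 5.4 prefers the scheduled visit in the by-visit safety tables too, so a transient abnormality found at an unscheduled visit can be missing from Tables 14, 16, 19, 20 and 21

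*SAP*

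**What the plan says.** SAP 5.4 has three parts. If an assessment exists at both kinds of visit, "the assessments from the scheduled visit will be considered in the analysis and tabular summaries". Otherwise, "if an assessment is completed only at supplementary visits, then the assessments from the most recent supplementary visit will be included". Finally, "Results of all assessments, including those performed during supplementary visits, will be included in the listings". Nothing in 5.4 limits it to efficacy, and nothing in SAP 13 or 14 exempts the safety summaries from it.

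Unscheduled visits are expected. Protocol 4.3 states: "For both cohorts, visits will occur at baseline, and then monthly and as clinically indicated".

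The assessment-based safety summaries are built by visit. In SAP 14.2 the number of participants losing 15 or more "letters from baseline at each follow-up visit will be included in Table 16". SAP 14.6 provides for "Number and percentage of participants experiencing optic nerve papilledema in each eye, headache classified by severity", shown in Table 20. SAP 13.2 (Table 14), 14.5 (Table 19) and 14.7 (Table 21) work the same way. The shells for these tables have rows for Baseline and Months 1 to 3 only.

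Adverse events are handled separately in SAP 12.1: "AEs reported throughout the study period will be presented in a listing with details", and "Total number and percentage of participants with AEs will be summarized by cohort and overall". The shells for Tables 12 and 13 have no visit rows.

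**The concern.** Preferring the scheduled value is sensible for efficacy, because it keeps measurement times comparable. For safety it works the other way. A clinically indicated visit is prompted by a possible problem, so it is where a transient toxicity is most likely to be seen. A scheduled visit some weeks later may find it resolved. Choosing the scheduled value then favours the recovered result, and choosing the most recent of several supplementary values does the same.

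The five tables cover risks that the protocol itself names: liver effects and raised intracranial pressure (5.3), headache and papilledema (4.4.3), liver function monitoring (4.3), and loss of 15 or more letters as a reason for withdrawal (7.1). Safety is part of the stated objective. Cohort 2 takes 48,000 IU daily against 16,000 IU in Cohort 1, and has no scheduled visit between the start of dosing and the treatment completion visit.

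**Working it through.** The plan gives no figure to reproduce here. The check sets the rule against the visit schedule and the table shells, then scales the effect.

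**1. Which safety tables the rule reaches.** Tables 12 and 13 count events and participants over the whole study with no visit rows, so 5.4 does not filter them. Tables 14 to 21 (eight tables) are by visit and fall under it. Of those, 15, 17 and 18 present RIT, LLVA and LLQ, which are efficacy measures. That leaves 14, 16, 19, 20 and 21 as the by-visit safety tables. None of their shells has an unscheduled-visit row or a worst-post-baseline row.

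**2. Where unscheduled checks can fall** (Protocol Appendix 2; SAP 3.1).
- Cohort 1: dosing runs from baseline to Month 2. One scheduled visit (Month 1) lies strictly between first dose and treatment completion.
- Cohort 2: dosing runs from baseline to Month 1. No scheduled visit lies strictly between. With a target of day 30 and a window of 14 days either side, Month 1 can fall from day 30 − 14 = 16 to day 30 + 14 = 44. Any post-baseline check before it is supplementary. The Month 1 check itself is scheduled and tabulated.

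**3. What happens to a transient finding.** Suppose a Cohort 2 participant has an abnormal result at an unscheduled visit before Month 1.
- Month 1 is attended and normal: the tables use the Month 1 value, and the abnormal result appears in the listings only.
- Month 1 is missed, with two supplementary checks, the first abnormal and the second normal: the second is used, being the most recent.
- Month 1 is missed, with one supplementary check, abnormal: it is tabulated.
- The finding is recorded as an adverse event: it is counted in Tables 12 and 13 in every case.

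SAP 5.4 does not say to which scheduled row a supplementary result is matched. This does not change the first case: either the result is displaced by the Month 1 value or it has no row of its own.

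**4. Scale (illustration, not a figure from the documents).** The safety population is everyone who takes at least one dose (SAP 5.2). SAP 5.1 aims at five analysed per cohort and allows up to ten enrolled in Cohort 2, so five and ten are used as the range. Intervals are exact (Clopper-Pearson) 95%.
- n = 5: shown 0/5 = 0% (0% to 52%); any-time count 1/5 = 20% (0.5% to 72%).
- n = 10: shown 0/10 = 0% (0% to 31%); any-time count 1/10 = 10% (0.3% to 44.5%).

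One displaced case therefore moves a cell by 20 or 10 percentage points. The intervals overlap widely, so the effect is on whether a case is visible in the table, not on the precision of a rate.

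**The case against.** The strongest reply is that nothing is lost. Adverse events from any visit go into Tables 12 and 13, split by severity, eye, outcome and relatedness. Every result, supplementary ones included, is listed. Results that exist only at supplementary visits are tabulated, which helps with a participant who stops before Month 1 and so has no scheduled follow-up value. Early discontinuation for safety is also counted in Table 1. In an exploratory, uncontrolled pilot of at most 18 participants, a reader can go through the listings case by case.

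Most of this stands, and it rules out three stronger readings. A reader might infer that toxicity found at an unscheduled visit does not reach the safety tables at all; Tables 12 and 13 contradict that. A reader might infer that a scheduled visit overrides every supplementary one; the rule applies to duplicates only. A reader might infer that all Cohort 2 safety data collected on supplement are lost from the tables; the Month 1 check at the end of dosing is scheduled, and adverse events are unaffected.

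The reply is still incomplete. The supplied documents give no rule for when an abnormal laboratory value, acuity, IOP or fundus finding must be recorded as an adverse event, so entry into Tables 12 and 13 cannot be assumed. SAP 13.1 treats natural-progression events separately: they are listed, and summarised only if there are enough data, so a retinal finding classified that way may miss both tables. And where a finding is recorded as an adverse event, Table 12 or 13 can count it while the by-visit table for the same parameter shows none, with nothing to reconcile the two.

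**Conclusion.** The point holds for Tables 14, 16, 19, 20 and 21. As written, 5.4 keeps a transient abnormality from a clinically indicated visit out of these tables when a scheduled value exists, and prefers the latest to the worst value when only supplementary visits exist. No other row restores it.

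The effect is on how safety is summarised, not on whether the data are reported, since the listings hold everything. Its size is one case shown as 0/5 instead of 1/5, or 0/10 instead of 1/10. That rests on assuming one such case; the documents report none. It also matters mainly for findings not recorded as adverse events, and how often that would happen cannot be judged from the documents. The change is worth making because it is cheap and the tables concerned cover the protocol's own named risks.

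**What to change.** Keep the 5.4 rule for efficacy analyses and for the by-visit rows of all tables, and say so in 5.4. Add to Tables 14, 16, 19, 20 and 21 an *any time after first dose* summary for each safety parameter, in the safety population. It would count participants with an abnormal or worst post-baseline result, using scheduled and supplementary visits together.

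Define worst for each parameter in advance, for example:
- highest IOP;
- any loss of 15 or more letters from baseline;
- any papilledema;
- most severe headache;
- any clinically significant laboratory change from baseline.

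Table 21 needs its own definition for each finding. Splitting the summary into on-supplement and after-supplement periods is optional.

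The cost is a short SAP revision, some extra programming and several added rows, most of them in Table 21, which has many parameters by eye and cohort. No new data are needed, because the supplementary results are already collected for the listings.

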5.5 Handling of Missing Values

In general, missing observations will be excluded from analyses. If a participant receives standard-of-care treatment for neovascular AMD in the study eye during the course of the study, the participant will be withdrawn from the study and the last observation will be carried forward for data analyses. This would be identified manually by reviewing the AEs and natural progression of disease events because it is not included as a termination reason in the case report form.

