4.4.3 Concomitant Therapy

Participants in both cohorts may continue to receive all medications and standard treatments administered for their conditions at the discretion of their treating physician, except for high-dose vitamin A palmitate supplementation ($\geq 8,000$ IU per day). A participant will be withdrawn from the study if placed on a daily dose of $\geq 8,000$ IU of vitamin A palmitate.

There are no pharmacologic interactions known to occur between vitamin A palmitate and tetracyclines, but there is the potential for additive side effects as each drug has the potential to cause intracranial hypertension. One case report in a patient receiving high doses of vitamin A palmitate combined with minocycline reported the development of benign intracranial hypertension.²⁴ For this reason, regular ophthalmic examinations during study visits is the

recommended care for participants receiving the drug combination. Specific questions regarding headaches and attention to optic nerve for presence of papilledema will be noted at each visit.

If participants are on Coumadin® at enrollment, they must visit their prescribing physician to check their Coumadin® status within 2-4 weeks after initiating study supplementation to have their Coumadin® regimen adjusted if necessary (as taking vitamin A palmitate and Coumadin® can increase the chances of bruising and bleeding.)

All participants are eligible to receive standard-of-care treatment for AMD while enrolled in this study. However, if a participant develops neovascular AMD in the study eye during the course of the study, the participant may receive standard-of-care treatment for neovascular AMD according to the recommendations of the participant's treating retina specialist. The participant will be withdrawn from this study and the last observation will be carried forward for data analyses.

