7.1 Participant Withdrawal Criteria

Participation in the study is strictly voluntary. Participants may choose to withdraw from this study for any reason at any time without penalty, without loss of benefits or prohibition from enrolling in other clinical protocols. All participants will be included in the analyses at the end of the study.

The investigator may withdraw a participant at his/her discretion for the following reasons:

- Investigator determination that study continuation is not in the best medical interest of the participant;
- Findings in the course of the trial that may affect willingness to participate;
- Participant requiring additional medicines that will interfere with the study supplement;
- Serious suspected adverse reaction;
- Visual acuity loss of ≥ 15 letters from baseline;
- Any other safety concerns;
- Participant unable to meet the criteria required for continued participation;
- Participant stops taking the IP before the primary outcome is assessed;
- Participant is taking daily dose of $\geq 8,000$ IU of vitamin A palmitate in addition to study supplement;
- Participant receives standard-of-care treatment for neovascular AMD in the study eye;
- Participant is unable to complete the AdaptDx™ test;
- Participant was in the first cohort and had his/her last intake of vitamin A palmitate less than two months prior to enrolling in the second cohort.

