10.3 Dark Adaptation Times

A similar analysis to the primary outcome analysis for dark adaptation times described in Section 9.1 will be conducted comparing baseline to post-treatment follow-up visit in each cohort (Table 9, Listing 1).

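### The carry-forward rule for participants treated for neovascular AMD puts an end-of-supplement value into the off-supplement follow-up visit (minor)

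*SAP*

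**What the plan says.** The default in SAP 5.5 is "In general, missing observations will be excluded from analyses". One exception follows. If the study eye is treated for neovascular AMD, "the participant will be withdrawn from the study and the last observation will be carried forward for data analyses". Protocol 4.4.3 has the same rule: "The participant will be withdrawn from this study and the last observation will be carried forward for data analyses". Neither document gives a reason for the exception or says which visits or tables it covers. SAP 5.5 adds that such cases must be found by manual review, because the case report form has no matching termination reason.

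Three other SAP sections decide what the rule does:
- SAP 5.2 defines the set used for the primary, secondary and exploratory outcome analyses: "Includes all enrolled participants who receive investigational product (IP) through the treatment completion visit".
- SAP 4.0 defines the post-treatment follow-up as "The final study visit which occurs one month after completion of treatment" (Month 3 in Cohort 1, Month 2 in Cohort 2).
- SAP 10.3 repeats the primary test at that visit: "dark adaptation times described in Section 9.1 will be conducted comparing baseline to post-treatment follow-up visit in each cohort". SAP 11.1 to 11.3 also use that visit, for Model 1 in Cohort 1 and for the LLVA and LLQ tests.

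On who is analysed, Protocol 7.1 says: "All participants will be included in the analyses at the end of the study". On withdrawal, it lists treatment for neovascular AMD in the study eye under "The investigator may withdraw a participant at his/her discretion for the following reasons", whereas SAP 5.5 and Protocol 4.4.3 state withdrawal as certain.

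**The concern.** The comparison of baseline with follow-up describes dark adaptation after the supplement has been stopped for a month. A value carried from the end of supplementation makes the affected participant's follow-up change equal to the completion change. That assumes full persistence in the one comparison meant to look at persistence. With five participants planned per cohort, a single carried value is a fifth of the mean. What is at stake is the estimate and its interpretation, in secondary and exploratory results.

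A second, smaller issue is that the protocol and SAP describe the analysed participants differently. This matters here because the analysed set determines which visits the carry-forward can reach.

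**Working it through.** The plan gives no effect size, SD, power or neovascular AMD rate, so it has no figure to reproduce. The five per cohort comes from SAP 5.1. Effect sizes, persistence and event rates below are assumptions, shown as ranges.

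**1. Which visit can be filled.** A participant withdrawn before treatment completion is outside the SAP 5.2 set and so outside Tables 9 to 11. For a participant inside it, the only scheduled visit left is the post-treatment follow-up.

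**2. Which value is carried.** The last scheduled observation is the treatment completion value, taken at the end of supplementation. There are two exceptions. Protocol 4.3 allows visits when clinically indicated, and SAP 5.4 uses a supplementary-visit value when no scheduled one exists, so an off-supplement measurement could be available. If the completion measurement was itself missed, an earlier value would be carried.

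**3. Shift in the follow-up mean.** Let d be the affected participant's change at completion and p the share that truly persists a month later. The true follow-up change is pd and the carried one is d. With n = 5 the mean shifts by (d − pd)/5 = (1−p)d/5.

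| p | Shift, as a share of d |
|---|---|
| 0 | 20% |
| 0.25 | 15% |
| 0.5 | 10% |
| 1 | 0% |

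At p = 0, assumed d of −2, −5 and −10 minutes gives shifts of −0.4, −1.0 and −2.0 minutes. If d is near zero, so is the shift.

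**4. Model 1 (Cohort 1).** Assume visits at months 0, 2 and 3, a random intercept, independent errors, a common change D at Month 2 and complete wash-out at Month 3. The slope weights are −5/14, 1/14 and 4/14.
- No carried value: slope D/14 = 0.071D per month.
- The carried participant: (1/14 + 4/14)D = 0.357D.
- Mean of four and one: (4 × 0.071 + 0.357)D/5 = 0.129D.
- Modelled Month 3 difference (three times the slope): from 0.21D to 0.39D.

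**5. Chance of a case in Cohort 2.** Five participants at risk for about one month each give 1 − exp(−r × 5/12). Assumed rates r of 2%, 5% and 10% per study eye per year give 0.8%, 2.1% and 4.1%. The result scales roughly with the month assumed.

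**6. Type I error.** I simulated four changes from N(0,1) and a fifth from N(d,1), with a two-sided t-test on 4 degrees of freedom and 2,000,000 runs per setting. Rejection was 4.9%, 4.0% and 2.4% for d of 1, 2 and 3 SD. The outlying value raises the SD as well as the mean.

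**7. Price of leaving the value missing.** The 95% CI half-width is 2.776/√5 = 1.24 SD at n = 5 and 3.182/√4 = 1.59 SD at n = 4. If exclusion is unbiased, mean squared errors are equal when 1/5 + (x/5)² = 1/4, where x = (1−p)d in SD units. Then x = √1.25 = 1.118, and carrying forward has the lower mean squared error below that.

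**8. Analysed set.** Protocol 7.1 includes everyone and names no table. SAP 5.2 restricts Tables 9 to 11, and SAP 15.0 does not explain the difference. SAP 14.0, 14.1, 14.3 and 14.4 present RIT, LLVA and LLQ by participant and visit for everyone dosed. If Protocol 7.1 were applied literally to Table 9, one neovascular case withdrawn before completion with baseline carried would enter the primary mean as zero change: five participants at D and one at 0 give 5D/6 = 0.83D.

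**The case against.** The rule is pre-specified, worded alike in both documents and confined to one event, so choosing it over exclusion is a choice of method. Exclusion has its own weakness: an eye that has just become neovascular is not missing at random, and dropping it may flatter the result. The efficiency argument can also favour carrying forward. Protocol 1.0 reports no significant improvement in Cohort 1. If that rests on a two-sided paired t-test in five participants (an assumption), the mean improvement was below 1.24 SD. Then x is under 1.118 for any p above 1 − 1.118/1.24 = 0.10.

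A reader might also infer that the bias always favours a lasting benefit. The documents do not support that. The affected eye need not share the cohort's mean change. Protocol 1.0 links greater AMD severity with longer RIT, so its completion value may already be worse. Protocol 3.2.1 admits eyes beyond the 40-minute test ceiling, where no change may be measurable.

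These points stand and set the limits of the concern. They do not remove it. Low mean squared error is little comfort when the imputed value assumes the answer to the question being asked, and the Cohort 1 result does not fix the effect at Cohort 2's different dose. The informative-exclusion point is a reason to show the case individually; it does not justify relabelling an on-supplement value as an off-supplement one.

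On the analysed set, the objection largely succeeds. The SAP 5.2 set fits a design that enrols to obtain five analysable participants per cohort and allows replacement in Cohort 2, and Protocol 7.1 can be read as met by the SAP 14 presentations. No passage says so, which leaves only a reconciliation.

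**Conclusion.** The concern holds as a minor point. When triggered, and without an off-supplement measurement from an unscheduled visit, the rule enters an end-of-supplement value at a visit defined as off supplement. One case in five moves the follow-up mean by up to a fifth of that participant's on-supplement change, for p between 0 and 1. The shift is towards persistence if that eye had improved; otherwise its direction is not known. No case is the likely outcome, choroidal neovascularization is excluded at entry, all analyses are labelled exploratory, and Listing 1 shows individual RIT values.

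Three further inferences would go too far:
- The primary comparison is not affected under the SAP 5.2 set.
- The chance of a case should not be computed over both cohorts as if prospective. Cohort 1 enrolment closed in May 2019 with three months of participation, so any case there is already known.
- The SAP does not discard the data of participants who stop early; it presents them in SAP 14 without tests.

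**What to change.** - **Carry-forward.** Delete the clause from SAP 5.5 and the data-analysis wording from the last sentence of Protocol 4.4.3, leaving the clinical wording unchanged. Analyse observed values at their own visit, leave later visits missing under the general rule in SAP 5.5, and list each case with its reason. Read that listing beside the follow-up mean, since excluding a progressing eye may be informative.
- **Analysed set.** Reconcile Protocol 7.1 with SAP 5.2. Keep the SAP 5.2 set as the main one for Tables 9 to 11 and state that the safety-population presentations in SAP 14 cover everyone dosed. Optionally add a supportive run of Tables 9 to 11 in all dosed participants with an observed value at the visit. It will add few values, especially in Cohort 2, where Month 1 is both the first scheduled post-baseline visit and treatment completion.
- **Withdrawal wording.** For this event, the certain wording in SAP 5.5 and Protocol 4.4.3 and the discretionary wording in Protocol 7.1 must be reconciled. No clinical rule is proposed here.

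The cost is SAP wording and a short protocol amendment, with no added visits or tests. Each case removes one follow-up observation, with the loss of precision shown in step 7, and gives up the lower mean squared error that carrying forward can have for small effects.
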